Tongue swab sensitivity and specificity: Tongue swab assay performance varies greatly depending on the studied population (e.g. high background prevalence, hospitalized, HIV), PCR method (manual vs. commercial PCR), location of oral sampling, and type of swab used. The sensitivity of tongue swabs ranges from 36.3% to 92.8%.^{50, 55} In a meta-analysis done by Wang et al., results from 23 studies found a pooled sensitivity of 50% (95%CI, 37-63%).⁵⁶ Tongue swab sensitivity in paediatric studies was lower (22%-43%) compared to adults.^{54, 57, 58} However, in PLHIV, tongue swab sensitivity of 81.3% compared to sputum Xpert Ultra and culture. Across studies, the specificity of oral swabs is very high with specificities of 100% in multiple studies.^{51, 58, 59} However, there is no data describing tongue swab yield, compared to yield in sputum in patients who either have early/minimal TB disease or aTB.

Acceptability of tongue swabs: Data from interviews with South African healthcare workers with extensive experience in sputum and swab collection indicated that they will prefer a tongue swab method above sputum collection, provided there is increased education to the public on this method to ensure cooperation from patients for sample collection.⁶⁰ However, the preferences of patients for either sputum or tongue swab or other specimen or diagnostic process has not been widely canvassed, especially when these are used to diagnose TB in those with either early/minimal TB disease or asymptomatic/subclinical TB. The effort, discomfort, and possible loss of privacy or dignity from collecting a specimen may impact on acceptability. Moreover, the value core believability that patients place on a laboratory result from a tongue swab may differ from that of a sputum specimen and may impact their willingness to start TB treatment if the test actually results as *M tuberculosis* complex detected.

T-CELL ANTIGEN-SPECIFIC ACTIVATION (TB-TASA)

Tuberculosis diagnosis remains challenging and is still widely dependent on sputum-based microbiological methods that miss or delayed many cases, especially asymptomatic, paucibacillary, paediatric, and extrapulmonary TB. T-cell antigen-specific activation assays are emerging as promising

non-sputum diagnostic tools⁶¹. These assays rely on stimulating whole blood or PBMC with *M. tuberculosis* antigens and measuring upregulation or loss of surface markers such as CD38, HLA-DR and CD27 on Mtb-specific T cells. Studies have shown that the presence of the MTB-specific activated T-cells indicates infection (latent or active, depending on clinical context).

However, larger evaluations are still needed to validate their performance, particularly in aTB.

MTB CELL FREE DNA

There is growing interest in blood-based (non-sputum) approaches that can detect fragments of circulating *Mycobacterium tuberculosis* as complementary or alternative diagnostic biomarkers. CRISPR-mediated detection platforms have emerged as promising tools due to their ability to amplify and detect short, low-abundance Mtb cfDNA fragments with high analytical sensitivity, potentially enabling non-sputum diagnosis and earlier detection⁶².

Several studies have demonstrated that Mtb cell free DNA (cfDNA) can be recovered from plasma and detected by CRISPR-based assays, where Cas12a complexes generate enzymatic signal amplification to improve detection of low concentrated target sequences. Huang et al, reported high diagnostic accuracy of Mtb cfDNA, with sensitivity of 96% (80-100) and specificity of 94% (71-100) in microbiologically and clinically confirmed HIV-negative TB cases, and sensitivity of 83% (36-100) and specificity of 95% (77-100) in paediatric and extrapulmonary cases. These findings support the potential Mtb cfDNA CRISPR-mediated assay as a rule-in test or as an adjunct to existing workflows.

Critical questions remain regarding their performance in detecting bacteriologically-confirmed aTB and whether they may be able to improve specificity and provide bacteriologic confirmation in people who would otherwise meet the definition of aTB-U.

2. OBJECTIVES

The **co-primary objectives** of the study are to compare Mtb infection, as defined by interferon release assay (IGRA) positivity, in child (2-14 years) household contacts of adults with bacteriologically-confirmed asymptomatic TB (aTB-C), with:

1. children in households with no adult with TB
2. children who are household contacts of adults with bacteriologically-confirmed symptomatic TB (sTB-C)

The **secondary objectives** are to:

1. Evaluate the diagnostic performance, feasibility, and acceptability of current tools for detecting aTB, including digital chest X-ray with computer-aided diagnosis (dCXR/CAD) and sputum Xpert, and sputum Mycobacteria Growth Indicator Tube (MGIT)
2. Evaluate the performance of novel diagnostic and screening tools to detect aTB including tongue swab NAAT, bioaerosol NAAT, exhaled breath condensate for lipoarabinomannan, cell free Mtb DNA and Mtb-specific T cell activation.
3. Characterize the features and longitudinal outcomes of sub-groups of people with aTB, including those with dCXR/CAD findings suggestive of TB but who are sputum Xpert & culture negative.

4. Establish a biobank and conduct studies of immune responses to understand the biology of aTB and define correlates of progression and resolution.
5. Model the contributions of aTB to global TB transmission and incidence and the potential impact of interventions to detect and treat this disease phenotype
6. Evaluate the proportion of child household contacts who convert from baseline negative to positive IGRA at 10-week visit or have a positive blood biomarker (including cell free DNA assay or positive Mtb-specific T cell activation assay).
7. Define the proportion of participants with TB screening results consistent with sTB-U who have a subsequent positive sputum Xpert, sputum MGIT, tongue swab NAAT or facemask NAAT.
8. Identification of transmission clusters using whole genome sequencing of Mtb strains obtained from participants with aTB-C, sTB-C and their household contacts.

3. METHODOLOGY

3.1 STUDY DESIGN

This is a multi-country, cross-sectional study designed to assess household Mtb infection and transmission among asymptomatic (aTB) and symptomatic TB (sTB) cases and their household contacts. Community-based screening will be implemented across contiguous geographic areas within each participating country. It is estimated that approximately 60,000 adults in Indonesia and 30,000 adults in South Africa will undergo screening. Eligible participants identified through community screening will be enrolled into the core study and related sub-studies for further diagnostic evaluation, clinical phenotyping, and biobanking. The core study is a **cross-sectional study comparing the Mtb infection status in child household contacts of people with aTB-C, sTB-C and community controls (randomly selected noTB)**. These households will be identified through **community-based TB screening**.

[figure not shown]
The **case-control phenotyping study** (*sub-study 1*) will be conducted in people with asymptomatic TB and identified controls in the core study and will comprise additional diagnostic tests, clinical phenotyping and biobanking.

A TB-U cohort study (*sub-study 2*) will be conducted in individuals identified during the community screening with bacteriologically unconfirmed TB that do not meet criteria for TB treatment, and will comprise serial clinical evaluation, diagnostic testing and biobanking.

A mathematical modelling study (*sub-study 3*) will utilize empiric data from the study to estimate the contribution of asymptomatic TB to local and global TB transmission and incidence and the impact of potential interventions.

The study flow chart provides an overview of the visit schedule and depicts how the core and sub-studies are interrelated ([Figure 1](#)).

Figure 1. Schematic representation of the study procedures and interrelations of the studies

The study is expected to be completed within 36 months following the grant funding award, with an anticipated 30-month implementation period. Implementation will commence in South Africa, followed approximately two months later by Indonesia, once site preparations are complete. A stage-gate review will be conducted when each country has screened around 20% of the target sample (approximately 5,000 participants in South Africa and 12,000 in Indonesia). At this point, estimated for August 2026 (South Africa) and October 2026 (Indonesia), key parameters informing sample size, including the number of aTB cases identified, number of child household contacts and child IGRA positivity across control, aTB, and sTB households, will be reviewed.

3.2 SETTINGS

This study will be conducted in contiguous geographical areas within:

1. King Cetshwayo and uMkhanyakude Districts, KwaZulu-Natal (KZN) Province, South Africa.

The study will start in the uMfolozi subdistrict (King Cetshwayo) and subsequently move to uMhlathuze (King Cetshwayo) and the Big Five Hlabisa subdistrict (uMkhanyakude), depending on enrolment progress and the stage-gate review.
2. Bandung City, West of Java Province, Indonesia

3.3 STUDY POPULATION

The study population for the **cross-sectional study of household Mtb infection (core study)** will be adolescents and adults (≥ 15 years) who undergo community screening. In addition, the core study will also enrol child household contacts (2–14 years) of community-screened adolescents and adults who meet the inclusion criteria for the core study (aTB-C, sTB-C, or noTB)

In the **case-controlled phenotyping study (sub-study 1)** the study population are adolescents and adults with aTB-C, sTB-C or no TB controls who participated in the cross-sectional study (core study)

In the **TB-U cohort study (sub-study 2)** the study population are adolescents and adults (≥ 15 years) who were identified through the community TB screening as having TB-U.

The **study population and eligibility criteria** for each of the studies are defined below ([Table 1](#))

Table 1: Study Populations and Eligibility Criteria for the individual studies

Study	Study Population	Eligibility Criteria
Cross-sectional study of Household Mtb infection (core study)	
Community screening: Adolescents and adults (≥ 15 years) who reside in households located within the study areas in each setting
 
Child contacts: Children (2-14 years) who are household contacts of people with sTB-C, people with aTB-C or of randomly selected adults in households without TB
	
1. Adolescent/Adult participants for community screening
 
Inclusion criteria:
 
 1. Age ≥ 15 years 2. Residence in the designated study area 3. Residence in a household with children (2-14 years) 
Exclusion criteria:
 
 1. Unable or unwilling to consent (>18 years) 2. Unable to unwilling to assent (15-17 years) 3. Parent or guardian unwilling to consent (15-17 years) 4. Residence in a household with a participant in a TB vaccine trial (currently or previous 2 years) 
2. Child household contacts
 
Inclusion criteria:
 
 1. Age 2-14 years 2. Household residence with an adolescent/adult participant with: 
 a. aTB-C, or b. sTB-C, or c. an adolescent/adult participant who has been selected as a healthy control (no TB) 
Exclusion criteria:
 
 1. Unable or unwilling to assent (≥ 7 years) 2. Parent/guardian unable or unwilling to consent 3. Residence in household in which any resident has been diagnosed with TB within the past 2 years 4. Residence in a household with more than one adolescent/adult with current co-prevalent TB-C
Case-control phenotyping study (sub-study 1)	Adolescents and adults (≥ 15 years) who participated in cross-sectional study of household Mtb infection (core study)	
1. Participants with aTB-C
 
Inclusion criteria:
 
 1. Adolescent/adult participant in TB screening 2. Screening W4SS negative 3. Screening sputum Xpert positive (any grade) OR Mtb MGIT positive* OR tongue swab NAAT positive 
2. Participants with sTB-C
 
Inclusion criteria:
 
 1. Adolescent/adult participant in TB screening 2. Screening W4SS positive 3. Screening sputum Xpert positive (any grade) OR Mtb MGIT positive* OR tongue swab NAAT positive

Study	Study Population	Eligibility Criteria
		
3. Participants selected as healthy controls
 
Inclusion criteria
 
 1. Adolescent/adult participant in TB screening 2. Screening W4SS negative 3. Screening sputum Xpert negative; AND Mtb MGIT negative* 4. Selected as a healthy control in the Cross-sectional study of Mtb infection in households (see above) 
ALL 3 groups above
 
Exclusion criteria
 
 1. Unable or unwilling to consent 
* MGIT results returning after enrolment may result in study group re-categorisation

Cohort study (sub-study 2)	Adolescents and adults (≥ 15 years) who participated in TB screening.	
Participants who meet the study case definition for bacteriologically-unconfirmed TB (TB-U)
 
Inclusion criteria:
 
 1. Adolescent/adult participant in TB screening 2. All three sputa Xpert are negative/ ‘trace’ AND all three sputum are Mtb MGIT negative 3. Screening dCXR/CAD interpretation is “suggestive of TB” 4. Clinical assessment at phenotyping visit does not suggest a non-TB aetiology for dCXR/CAD findings and is consistent with TB-U 5. Participant did not commence TB treatment after phenotyping visit 
Exclusion criteria
 
 1. Unable or unwilling to consent to longitudinal follow-up

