	
household contact IGRA positivity between aTB-C and sTB-C index cases is 0.90, 150 index cases of each TB phenotype in each setting will give us $\geq 80\%$ power to demonstrate that the transmission risk with aTB-C is not less than 50% of the transmission risk of sTB-C.
 
The index adults from the 600 households in each setting will be enrolled in the case-control phenotyping study. Assuming that the true sensitivity and specificity of the diagnostic tools are between 70-95%, with 150 aTB-C and 150 sTB-C cases, we will be able to estimate the sensitivity with a precision of $\pm 7.6\%$ to $\pm 4\%$. With 300 controls, we will be able to estimate the specificity with a precision of $\pm 5.3\%$ to $\pm 2.6\%$.
 
In each setting, after community screening, we expect to identify 500 participants with aTB-U who are eligible for the TB-U cohort. Based on the assumed annual progression rate, this sample size is expected to yield 31-66 individuals with progressive disease. With 50 individuals who progress and 100 who do not, we will have $\geq 80\%$ power to detect a difference of 0.50 standard deviations in mean biomarker concentrations between the two groups. If the prevalence of biomarkers in individuals who do not progress is 10-20%, we would have $\geq 80\%$ power to detect an increase to 30-40%.

Study Population	
Cross-sectional study of household Mtb infection (core study)
 
 • Community screening: Adolescents and adults (≥ 15 years) who reside in households with children 2-14 years and located within the study areas in each setting. • Child contacts: Children (2-14 years) who are household contacts of participants with aTB-C, sTB-C, or of randomly selected neighbourhood households with adults without TB 
Case-control phenotyping study (sub-study 1) Adolescents and adults (≥ 15 years) who were identified through community TB screening to have aTB-C, sTB-C and no TB
 
Cohort (sub-study 2) Adolescents and adults (≥ 15 years) who were identified through community TB screening with bacteriologically-unconfirmed TB (TB-U)

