In addition, a digital chest X-ray with computer-aided detection (dCXR/CAD) will be conducted as part of the TB screening assessment. All dCXR/CAD X-Rays which are reported as suggestive of TB by the CAD software will be reviewed by a radiologist.

Within 2 weeks of the screening visit (visit 1.0), the **adolescent/adults** screened will be categorised into one of 5 screening groups ([Figure 2](#)).

- (1) **aTB-C Participant:** W4SS screening - negative; Xpert -positive (any grade) OR tongue swab-NAAT – positive; dCXR/CAD – any result
- (2) **sTB-C Participant:** W4SS screening - positive; Xpert -positive (any grade) OR tongue swab-NAAT – positive ; dCXR/CAD - any result
- (3) **aTB-U Participant:** W4SS screening - negative; Xpert -negative-OR tongue-swab NAAT – negative; dCXR/CAD – suggestive of TB
- (4) **sTB-U Participant:** W4SS screening -positive; Xpert-negative OR tongue-swab NAAT – negative; dCXR/CAD – suggestive of TB
- (5) **noTB Participant:** W4SS screening -negative; Xpert – negative OR tongue swab NAAT – negative ; dXR/CAD – normal

Adult and adolescent participants (≥15 years) will be identified ([Figure 2](#)) for potential enrolment into either the case-control phenotyping-study (Sub-study 1; aTB-C, sTB-C) or the TB-U cohort study (Sub-study 2; TB-U). For each aTB-C participant, a control participant (1:2 ratio) will be randomly selected among noTB participants within the neighbourhood (250–700 m radius depending on the population density, using GIS coordinates) of the aTB-C participant's household.

The **child household contacts (aged 2–14 years)** of those with aTB-C and their controls, and sTB-C will be eligible for inclusion in the cross-sectional study (IGRA assessments) of household Mtb infection (core study).

[figure not shown]

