Most participants will be categorized according to their screening results which include Xpert or tongue swab NAAT and dCXR/CAD. These results are expected to be available within approximately two weeks of sample collection. The **MGIT culture results** may require up to 6 weeks to become available.-Those participants that are newly diagnosed with TB (as aTB-C, sTB-C) based on the MGIT culture results will be considered for the sub-study 1 and 2; while their child household contacts will be invited to undergo IGRA assessments. If the adolescent or adult MGIT result is positive within 2 weeks of collection, the child HHC will be invited to participate in visits 2.1 and 2.2. If the MGIT result becomes positive later than 2 weeks, only visit 2.2 will be conducted, due to study visit scheduling constraints.

All adolescent/adult participants with positive screening results (Xpert; tongue swab, MGIT) will be referred to Visit 1.1 within 2 weeks of their positive result and will receive appropriate referrals at the end of the study visit. Participants who are not eligible for any additional study visits will have their screening results returned, appropriate referrals will be made as needed, and participants will be thanked for their participation. When all results are normal and no referrals are required, participants may be informed of their results by telephone or SMS.

Households of **aTB-C participants (aTB-C household)** and **sTB-C participants (sTB-C household)**, as well as selected **noTB participants (Control Household)** serving as controls, will undergo a follow-up visit (Visit 2.1).

At the **community or clinic visit (visit 2.1; Figure 3)**, if the child or children meet the eligibility criteria, initially parental/individual assent and/or guardian consent will be obtained for each child during this visit.

Figure 3. Core study participant flow, including IGRA testing among child contacts.

★ If the adolescent/adult MGIT is positive within 2 weeks, the child household contact will be eligible for both visit 2.1 and 2.2

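### Co-primary objective 1 needs control households with no TB, but the selection and eligibility rules test one noTB adult and still admit a household with one TB-C co-resident

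*Protocol*

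**What the plan says.** **Where the comparator is a household without TB**
- Section 2, co-primary objective 1: "children in households with no adult with TB".
- Section 3.3, Table 1, study population cell of the core study: contacts of "people with aTB-C or of randomly selected adults in households without TB".
- Background, Geographical setting: the 7% IGRA positivity used for KwaZulu-Natal controls comes from community controls with nobody in the household with TB.
- The Protocol Summary is ambiguous: "randomly selected neighbourhood households with adults without TB".

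**Where the rule is about one person**
- Section 3.5: "a control participant (1:2 ratio) will be randomly selected among noTB participants within the neighbourhood", within 250-700 m of the aTB-C home. The home of the person selected becomes the control household.
- Table 1, child inclusion 2c: residence with "an adolescent/adult participant who has been selected as a healthy control (no TB". Nothing is asked about the other adults.

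**The two exclusions that concern co-residents**
- Child exclusion 3: "Residence in household in which any resident has been diagnosed with TB within the past 2 years".
- Child exclusion 4: "Residence in a household with more than one adolescent/adult with current co-prevalent TB-C".

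Both exclusions apply in the same words to aTB-C, sTB-C and control households. Neither mentions TB-U.

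**The concern.** All adolescents and adults in a household are approached for screening (Section 3.5), so a noTB adult can share a home with an adult found to have TB-C or TB-U. Under the itemised rules that noTB adult can still be drawn as a control, and the children of the home then count as unexposed. If those children have been infected by the co-resident, control IGRA positivity rises and the aTB-control risk difference shrinks, which works against detecting transmission from aTB.

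Group membership is also left open. A child living with one TB-C adult and one selected noTB adult meets inclusion 2a or 2b and also 2c, and no rule says which prevails. The study's timing makes this a practical matter: control households are visited in weeks 0-2, while MGIT results may take up to 6 weeks. Eligibility and control selection belong in the protocol, so this is not a detail that can wait for an analysis plan.

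**Working it through.** **1. Do the exclusions close the gap?**

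Exclusion 4 removes households with two or more TB-C adults, so it allows none or one. In a case household the one allowed is the index. In a control household it is an exposure that the objective rules out.

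Exclusion 3 is worded identically for all three groups. If it covered diagnoses made by the study's own screening, every aTB-C and sTB-C household would be excluded too. It must therefore mean diagnoses before screening, and so it does not reach TB found at screening.

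The Table 1 footnote on re-categorisation after MGIT belongs to sub-study 1 and concerns the adult participant. It gives no rule for the children or the household in the core study.

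**2. The plan's own figure**

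Section 5.1 and Table 4 give 80% power in KwaZulu-Natal for 14% against 7%, with 150 and 300 households, a mean of 2.5 children (SD 1.6) and ICC 0.30. I assume a two-sided 5% level, which is not stated for this comparison.

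- Design effect = 1 + [(1 + CV²)m − 1] × ICC = 1 + [(1 + (1.6/2.5)²) × 2.5 − 1] × 0.30 = 1.757
- Effective children in the aTB group = 150 × 2.5 / 1.757 = 213.4
- Power = 79.6%, which reproduces the stated 80%.

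For Bandung (32% against 20%, mean 1.5, SD 0.7) the design effect is 1.248, the effective number 180.3 and the power 85.9%. The stated 80% is conservative there.

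**3. How many control households could hold a TB-C adult?**

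Table 3 gives aTB prevalence of 0.50% (KwaZulu-Natal) and 0.25% (Bandung). The protocol states no sTB-C screening yield; 150 sTB-C is an enrolment target. I assume sTB-C is as frequent as aTB-C, so p = 1.0% and 0.5%. I also assume k = 1-3 other screened adults and independence within households.

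Share f = 1 − (1 − p)^k, multiplied by 300 control households:

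| Site | k = 1 | k = 2 | k = 3 | Households of 300 |
|---|---|---|---|---|
| KwaZulu-Natal | 1.0% | 2.0% | 3.0% | 3 to 9 |
| Bandung | 0.5% | 1.0% | 1.5% | 1.5 to 4.5 |

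**4. Effect on the risk difference**

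Dilution = f × (q − p0), where p0 is the planned control positivity and q is the positivity in affected homes. I take q between the aTB value in Table 4 and the sTB value in Table 3.

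- KwaZulu-Natal (p0 7%, q 14-18%): from 1.0% × 7 = 0.07 to 2.97% × 11 = 0.33 points
- Bandung (p0 20%, q 32-40%): from 0.5% × 12 = 0.06 to 1.49% × 20 = 0.30 points

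**5. Effect on power**

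- KwaZulu-Natal: 78-79% at f = 1% and 75-77% at f = 3%, against 79.6% with none
- Bandung: about 85% at f = 1% and 83-84% at f = 2%, against 85.9% with none

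**6. TB-U co-residents**

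The plan expects 500 TB-U participants per setting, or 500/30,000 = 1.67% and 500/60,000 = 0.83%. The same formula gives a TB-U co-resident in 1.7-4.9% of KwaZulu-Natal and 0.8-2.5% of Bandung control households. The protocol gives no IGRA positivity for children of TB-U adults, so I put no dilution on these.

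**The case against.** The strongest reply is that the intent is already in a defining place. Section 3.3 says that Table 1 defines both the populations and the eligibility criteria, and its population cell says households without TB. Section 3.5 also labels the homes of aTB-C and sTB-C participants as case households, so a home with a detected TB-C adult already carries a case label. This stands against one inference a reader might draw, that the plan has chosen a different comparator. It has not: the document contradicts itself, and the household condition was not carried into the selection step or the itemised criteria. The reply does not remove the gap, because nothing says that the case label overrides selection as a control.

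A reader might also infer that noTB relatives of the aTB-C index, who live inside the sampling radius, would be drawn as controls for their own household. The documents point the other way. The Protocol Summary counts 600 households per setting as 150 + 150 + 300, and Section 5.2 speaks of control houses in the same neighbourhood. Both imply separate households, although no rule says so.

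A third tempting reading is a dilution near one percentage point. That requires children of TB-U adults to have the full positivity of sTB-C households. The Background says such X-ray findings may reflect inactive treated TB or non-TB causes, so the larger figure is not supported.

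Finally, barring TB-U co-residents from control households alone has a cost. Case households would keep theirs, and any transmission from TB-U adults would then be credited to aTB-C. That is correct, and the fix has to deal with it.

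**Conclusion.** The point holds as a contradiction between the stated comparator of co-primary objective 1 and the rules meant to produce it, together with a missing precedence rule for mixed households. The expected numerical effect is small: about 0.1-0.3 percentage points of dilution from TB-C co-residents, against detectable differences of 7 points (KwaZulu-Natal) and 12 points (Bandung). It runs towards no difference as long as children in affected homes are at least as often IGRA positive as other control children. KwaZulu-Natal has little slack, since its power is just 80% as planned.

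The size rests on assumptions the protocol does not supply: 1-3 other screened adults per household, sTB-C as frequent as aTB-C, no household clustering of TB, and aTB- to sTB-household positivity in affected homes. Clustering would raise the counts. The change is worth making because it concerns a co-primary comparator and costs little, not because the bias is large.

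**What to change.** 1. In Section 3.5 and child inclusion 2c, select controls only from households in which no screened adolescent or adult has TB-C. This also excludes the index household.
2. Split child exclusion 4. For case households, exclude when more than one adult has TB-C. For control households, exclude when any adult has TB-C.
3. State that a TB-C diagnosis made later by MGIT in any adult of a control household removes that household from the control group.
4. Settle TB-U co-residents explicitly, in one of two ways. Either apply the no-TB condition to TB-U as well and name the asymmetry with case households, where TB-U co-residents remain. Or keep these households and add a sensitivity analysis that drops households with a TB-U co-resident from both groups.

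The cost is protocol wording and one household-level filter in the control selection, using results already collected. The control pool becomes slightly smaller and a control will occasionally have to be redrawn. Adults who decline screening remain of unknown status under any version of the rule.
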